#### Exclusion

- Pregnant or breast-feeding women
- Desire to be treated for any substance use disorder or court ordered to not drink alcohol
- Medical disorders or other conditions that may influence study outcome or subject safety
- Positive urine drug screen for amphetamines/ methamphetamines, barbiturates, benzodiazepines, cocaine, opiates, or phencyclidine
- Medications (past 30 days) that could influence subject data/subject safety (e.g. antidepressants, antipsychotics, benzodiazepines, etc.) as determined by [name]

[figure not shown]
- DSM 5 Disorders (non AUD) or current/history of neurological disease of cerebral origin, or head injury with > 20 min loss of consciousness
- Positive BrAC reading on arrival at any study visit
- Actively suicidal (for example, any suicide attempts within the past year or any current suicidal intent, including a plan) or are at serious suicidal risk, by clinical evaluation by the investigator
- Any condition for which the principal investigator determines it is unsafe or not prudent to enroll a subject.

#### 4.0 Enrollment/Randomization

The project employs a between-participants design. Each participant will undertake 3 or 4 sessions: an interview/screening session, 2 randomly counter-balanced (neutral and aversive stimuli) IV alcohol self-administration sessions, and in a subset of subjects that meet the criteria outlined in the fMRI screen, an fMRI resting state scan. All sessions will take place in the Neural Systems Laboratory at the Indiana Clinical Research Center at Indiana University Hospital or at the Neuroscience Center at Methodist Hospital.

We will consent 300 participants to enroll 150 and complete 100 participants: **a**) 50 individuals who are current drinkers with lower lifetime drinking history, between 25-50 kg ethanol, **b**) 50 individuals who are heavy drinkers with a higher lifetime drinking history of 250-500 kg ethanol, and **c**) individuals below 500 kg ethanol at the discretion of the principle investigator. We will target equal numbers of men and women for inclusion in the lower and higher lifetime drinking groups. Total participant payment will be \$400, plus parking/travel costs.

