## 2.0 Rationale and Specific Aims

Prolonged alcohol use results in neuroadaptations. The consequences include a decreased sensitivity to alcohol, a shift from positive to negative reinforcement-based alcohol use, increased negative affect that drives further consumption, and ultimately, aversion-resistant drinking (ARD; drinking despite resultant problems and adverse consequences). ARD is a hallmark of more severe and treatment-resistant compulsive use and is modeled well in preclinical research. There are, however, no well-validated models of human ARD and, little understanding of the neural signature underlying the transition to ARD. This project seeks to validate such a model and to examine its principal determinants in 100 subjects.

The development of ARD marks an important transition from treatment-sensitive to treatment-resistant drinking behaviors. This creates a critical need to develop an objective measure of ARD in humans and to characterize its neural functional substrates. We propose that alcohol seeking despite aversion (SDA) is an early marker of ARD in humans, attributable to the neuroadaptations caused by excessive exposure to alcohol. An objective measure of SDA in human alcohol use will lead to better understanding of the mechanisms of disease progression in humans and advance the translation between human and animal work.

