- Blood sample will be taken for future polygenic risk analysis
- Penn State Electronic Cigarette Dependence Index
- Wisconsin Card Sorting Task
- Slips of Action Task

Participants that complete the interview will be compensated \$25 and provided a parking pass or bus voucher. Participants that complete part of the interview remotely and appear to meet study criteria will be asked to visit the ICRC for a short visit where they will provide a blood sample, urine, and be paid the interview fee of \$25. Participants who complete only the online portion of the interview and are withdrawn from the study will be compensated with \$15 in the

form of an electronic or mailed gift card or mailed check. If there is a significant delay between the online and in-person portion of the interview, the subject may request compensation with \$15 in the form of an electronic or mailed gift card or check. Following the interview, the information collected during the interview will be evaluated and if the participant meets all study criteria, they will be contacted and asked to schedule the alcohol self-administration sessions, while a subset of participants will be asked to participate in the fMRI sessions. The figure below depicts the flowchart for the 2 alcohol self-administration sessions:

[figure not shown]

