### Power Analyses

Alcohol self-administration: Our previous alcohol self-administration work showed effect sizes from 0.49 to 1.31 according to the phenotype of interest. Neurophysiological correlates (EEG/fMRI): Published outcome and feedback-related differences in N200 and P300 amplitudes yield effect sizes from 0.78 to 2.12 for subjects with an AUD versus controls, and 0.62 to 1.6 for the effect of alcohol. There are no standards for power analyses in whole brain connectomics. However, our pilot data showed significant results in  $n=51$ , suggesting  $n=100$  is sufficient to find robust connectivity patterns. We will ensure robustness using permutation tests combined with an extent threshold, or alternatively, using the Permutation Network Framework. Relationship to AUD risk variables: In our pilot data, the relationship between SDA and AUD risk correlates ranged from  $r=0.32 - 0.63$ . With a sample of  $n=100$ , we can detect an effect size of at least 0.32 and still maintain adequate  $power=0.90$ ,  $\alpha=0.01$ . When categorized by groups of  $n=50$  (high/low lifetime drinking history), we can detect differences with an effect size of 0.64 and still maintain adequate  $power=0.90$ ,  $\alpha=0.01$ .

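### The connectivity analyses are justified with n=100, the whole-study completer target, although only a subset of unstated size is scanned

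*Combined protocol and SAP*

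**What the plan says.** **Study size.** Section 4.0 (Enrollment/Randomization) states: "We will consent 300 participants to enroll 150 and complete 100 participants". Section 2.0 gives the same total, saying the project will "examine its principal determinants in 100 subjects".

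**Who is scanned.** Section 4.0 says "Each participant will undertake 3 or 4 sessions". Three of these are the screening interview and the two self-administration sessions. The fourth is the scan, done "in a subset of subjects that meet the criteria outlined in the fMRI screen, an fMRI resting state scan". Section 5.0 (Study Procedures) describes the invitation to self-administration after screening, "while a subset of participants will be asked to participate in the fMRI sessions". Neither section says how large the subset is.

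**Sample-size argument for imaging.** Power Analyses, within the statistical section, says that no standard power method exists for whole-brain connectomics. It then cites significant pilot results in 51 people, "suggesting $n=100$ is sufficient to find robust connectivity patterns". No effect size, alpha or power is attached to this sentence.

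**What is tested.** Hypothesis 6a relates network segregation to SDA through permutation tests with a two-tailed 0.05 threshold and an extent threshold. Hypothesis 6b correlates ventral striatal seed connectivity with SDA voxel by voxel, with false discovery rate control. The plan for hypothesis 1 defines SDA as work for alcohol in the aversive session.

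**The concern.** The n=100 in the imaging sentence is the number of people meant to complete the study, not the number meant to be scanned. The sentence has no calculation behind it. Its force lies in 100 being roughly twice the pilot size of 51. If the analysed number is smaller, that margin is smaller, and the plan does not say by how much.

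Hypotheses 6a and 6b are the only fMRI tests in Aim 3. A reader relying on Power Analyses would take them to be supported by 100 participants. The results would also describe people who passed the fMRI screen, a narrower group than the cohort in which SDA is otherwise characterised.

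**Working it through.** **Step 1: the plan's own figure.** The imaging n=100 cannot be reproduced, because it comes with no effect size, alpha or power. It can only be compared with the design.

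**Step 2: the sections side by side.**

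| Item | Value | Where |
|---|---|---|
| Planned completers | 100 (of 150 enrolled) | Section 4.0 |
| Sessions per person | 3 or 4; the scan is the optional one | Section 4.0 |
| Number scanned | a subset, size not stated | Sections 4.0 and 5.0 |
| n relied on for connectivity | 100 | Power Analyses |

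A participant can finish with three sessions and no scan. Reaching 100 scans from 100 completers would need every completer to be scanned, which contradicts a subset.

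**Step 3: what else bears on the analysed number.**
- Section 3.0 lists no MRI-specific exclusion, so a person who fails the fMRI screen can still enrol and count among the 100.
- Section 5.0 repeats drug, pregnancy and breath-alcohol screening before imaging and stops the scan for any discomfort.
- Both hypotheses need SDA, so only people with a usable scan and an aversive session contribute.
- The plan gives no allowance for unusable scans and no rule to recruit until a scan target is met.

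**Step 4: completers needed for 100 scans.** The scanned share is an assumption. Completers needed = 100 / share, rounded up.
- 90%: 100/0.9 = 111.1, so 112
- 80%: 100/0.8 = 125
- 60%: 100/0.6 = 166.7, so 167
- 50%: 100/0.5 = 200

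The plan has 100.

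**Step 5: illustration of how precision depends on n.** For one correlation, using Fisher's z, two-sided alpha 0.05 and 90% power:

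detectable r = tanh[(1.960 + 1.282) / √(n − 3)]

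| Assumed n | (1.960 + 1.282)/√(n − 3) | Detectable r |
|---|---|---|
| 100 | 3.242/9.849 = 0.329 | 0.318 |
| 80 | 3.242/8.775 = 0.369 | 0.353 |
| 60 | 3.242/7.550 = 0.429 | 0.405 |
| 50 | 3.242/6.856 = 0.473 | 0.440 |

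Alpha 0.05 matches the threshold for hypothesis 6a. The 0.318 at n=100 should not be confused with the effect size of 0.32 in Power Analyses. That figure belongs to the correlations of SDA with AUD risk variables, is paired there with alpha 0.01, and is not an imaging figure. At that pairing (r=0.32, n=100, two-sided alpha 0.01) Fisher's z gives power Φ(0.332 × 9.849 − 2.576) = 0.755, not 0.90. That is a separate matter from this point.

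The table models neither the permutation and extent-threshold procedure of 6a nor the voxel-wise correction of 6b.

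**The case against.** Four arguments can be made for the plan.

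1. *A total of 100 scans is not excluded.* Section 4.0 lists 50 low-history and 50 high-history participants, which already makes 100, and adds an open-ended group admitted at the investigator's discretion. It also enrols 150, and the imaging subset is chosen after screening, not from completers. This stands against any claim that 100 is impossible. It does not rescue the sentence, because the plan states neither a larger completer total nor the use of scanned non-completers.

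2. *The plan makes no formal power claim for imaging.* It says that the pilot suggests 100 is enough, not that 100 is necessary, and on that reasoning any subset above 51 still exceeds the pilot. This stands. A reader might infer that the imaging analyses are shown to be underpowered, but the documents do not support that: they give neither an imaging effect size nor a scan count.

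3. *The scanned subset might be thought to be close to the pilot size.* Nothing supports that either. The pass rate of the fMRI screen is unknown.

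4. *The n=100 sentence follows a remark on whole-brain connectomics.* It therefore fits hypothesis 6a, and the seed-based 6b is covered only by implication. This stands. Hypothesis 6b then has no sample-size argument of its own.

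**Conclusion.** The sufficiency statement is wrong as written. It applies the whole-study completer target to analyses that the design confines to a scanned subset. On the planned 100 completers, the number with both a usable scan and an aversive session will be below 100.

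The size of the shortfall cannot be derived from the documents. The detectable correlations, from 0.32 at n=100 to 0.44 at n=50, rest on assumed subset sizes and a single-correlation model. They show the direction of the effect and imply nothing about the true imaging effect. The supported conclusion is that the imaging sample size is unstated and its stated justification does not match the design. Neither inadequate power nor the impossibility of 100 scans has been shown.

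**What to change.** In Power Analyses:
- Replace n=100 for the fMRI analyses with the expected number of participants who will have a usable scan and SDA data, and say how that number was reached.
- Give the single-correlation r detectable at that number, labelled as an illustration that does not represent the permutation or voxel-wise tests.
- Withdraw the statement that n=100 is sufficient for connectivity.
- Say explicitly whether the argument is meant to cover hypothesis 6b as well as 6a.

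In the plans for hypotheses 6a and 6b, state that the conclusions apply to the scanned subset. A table comparing scanned and unscanned completers on SDA, lifetime drinking, age and gender would be good practice but is optional.

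The cost is a few sentences of protocol text, and no change to recruitment or procedures. The downside is that the stated figure for the imaging part of Aim 3 becomes less favourable.

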#### 5.0 Study Procedures

**Recruiting.** Participants will be recruited by local advertisements and word of mouth and they will call the study line expressing interest, OR participants will be recruited from the Neural Systems Lab research registry (IRB# 1506904956), OR from the Indiana CTSI iConnect

[figure not shown]
research database. An in-depth phone interview will cover all inclusion/exclusion criteria for the study that can be garnered by conversation. Those who continue to be qualified will either 1) be scheduled for a face-to-face interview conducted at the Indiana (CTSI) Clinical Research Center (ICRC) where they will consent to participate in the study, or 2) arrange for a remote interview where they will consent to participate and complete interview measures electronically and converse with study staff via IU Zoom Health or similar secure platform.

*Screening.* The screening interview will include informed consent, assessment of inclusion/exclusion criteria, and an introduction to study procedures to familiarize participants with infusion and fMRI methods. All or some of the following measures will be collected during the screening interview, at the discretion of the principle investigator:

[figure not shown]
- The Alcohol Use Disorders Identification Test
- The Family History of Alcoholism Module of the SSAGA
- Family History Questionnaire
- The UPPS-P Impulsive Behaviors Scale measures impulsivity traits, including urgency.
- Self-Rating of Effect of Alcohol assessing retrospective sensitivity to the subjective response to alcohol.
- Center Epidemiologic Studies – Depression screening test
- Short Inventory of Problems – Revised
- Eysenck Personality Questionnaire
- Medical History (including menstrual phase for women)
- Fagerstrom Test for Nicotine Dependence
- The Semi-structured Assessment for the Genetics of Alcoholism – II, Alcohol, and any other modules as deemed necessary by the principle investigator
- Timeline Follow-back modified to assess for one- and five-week recall of alcohol use
- Concordia Lifetime Drinking Questionnaire
- Clinical Institute Withdrawal Assessment for Alcohol Scale
- Generalized Anxiety Disorder 7 Scale
- Urine pregnancy and drug screen (~50cc)
- Breath Alcohol Concentration Measurement
- Liver function assessment (~10cc)
- Brief Trauma Questionnaire, Primary Care PTSD Screen
- Impaired Control Scale
- fMRI screening form
- Alcohol Purchase Task
- Penn Alcohol Craving Scale
- Blood sample will be taken for future polygenic risk analysis
- Penn State Electronic Cigarette Dependence Index
- Wisconsin Card Sorting Task
- Slips of Action Task

Participants that complete the interview will be compensated \$25 and provided a parking pass or bus voucher. Participants that complete part of the interview remotely and appear to meet study criteria will be asked to visit the ICRC for a short visit where they will provide a blood sample, urine, and be paid the interview fee of \$25. Participants who complete only the online portion of the interview and are withdrawn from the study will be compensated with \$15 in the

form of an electronic or mailed gift card or mailed check. If there is a significant delay between the online and in-person portion of the interview, the subject may request compensation with \$15 in the form of an electronic or mailed gift card or check. Following the interview, the information collected during the interview will be evaluated and if the participant meets all study criteria, they will be contacted and asked to schedule the alcohol self-administration sessions, while a subset of participants will be asked to participate in the fMRI sessions. The figure below depicts the flowchart for the 2 alcohol self-administration sessions:

[figure not shown]

*IV alcohol self-administration protocol.* Upon arrival at the Indiana Clinical Research Center, participants will be re-screened for drug use and pregnancy, and BrAC. The participant's BrAC must be at 0 by the experiment start time. We will record the subject's recent drinking. Using sterile technique, an indwelling catheter will be placed in a vein of the ante-cubital fossa of one arm. A standardized breakfast will be served and phones and car keys held for safekeeping. The participant will be fitted with a 65-lead EasyCap® and seated in one of the lab's 5'x7' Industrial Acoustic Corporation® sound-dampened chambers, or in a private room designed for ERP data collection. A closed-loop intercom system enables the participant to talk to the technician at any time without manual effort. The participant will be instructed in the use of the Draeger® BrAC meter. Baseline electrophysiologic (discussed below) and subjective response measures will be performed before the participant is prompted for a bathroom break. A single tube combining the outputs of 2 IMED PCTX infusion pumps will be joined with the indwelling catheter. Subjects will be asked to identify a comfortable sound volume from one of five choices for potential use during the A-CAT. The Computer-assisted Alcohol Infusion System (CAIS) software, developed at IU through IARC support, will be used to control the alcohol infusion rate (Figure 2). CAIS ensures an identical incremental BrAC exposure for each reward delivered within and across participants; variation in BrAC profile is determined solely by a participant's behavior. Carefully controlled infusion avoids expectancy effects and the 3-fold range of peak breath alcohol concentrations (BrACs) across individuals occurring after oral administration (Figure 3). Our IV alcohol administration techniques also achieve key features impossible to safely achieve with oral challenges. BrAC immediately descends upon termination of the infusion; after ingestion, the BrAC continues to increase until absorption is complete. CAIS continuously estimates the future time course of BrAC and prohibits infusion that would yield a BrAC exceeding the predetermined, ecologically valid safety limit (180 mg/dL for this project).

**Figure 2.**

[figure not shown]
Schematic of CAIS system, including computer specifications, software, and accessories.

**Figure 3.** *Left:* variability in breath alcohol concentration exposure trajectories from a controlled oral dose of alcohol in 44 participants. Each dosage was determined for the individual based upon their total body water, and administered under identical experimental conditions. *Right:* variability in breath alcohol concentration during a breath alcohol concentration clamp experiment when participants' breath alcohol concentrations were raised to 60mg% over 15 minutes and then maintained over 3 hours.

[figure not shown]
Prior to infusion, the participant's age, height, weight, and gender will be entered into the software, which transforms those measurements into parameters of the CAIS physiologically-based pharmacokinetic model of alcohol distribution and elimination. Computation of the infusion rate profile is based on these individualized model parameters to achieve identical incremental exposures to alcohol across participants. Each session begins with an approximately 30 min priming interval during which participants are clamped at 60 mg/dL. In the past we utilized either the investigator-prescribed exposure (BrAC clamping) or the participant-controlled Alcohol Self-Administration paradigm in our research. Here, we combine the 2 paradigms, employing our BrAC clamp as a priming exposure for an alcohol self-administration session. During the clamped priming interval, every participant will be maintained at a 60 mg/dL BrAC plateau for approximately 20 min; long enough to assess current sensitivity to alcohol in subjective and physiological domains. We will collect subjective responses to alcohol, a training run of a neutral SDA work task, and the Stop Signal Task at baseline and upon establishment of the BrAC plateau. Then, similar to our previous work, voluntary self-administration of alcohol or water begins, using the SDA innovation.

During the 2.5-hour alcohol self-administration, the participant chooses 1 of 2 rewards, either alcohol or water, at the voluntary initiation of the next work-set. The work schedules required to obtain the reward are identical, but progress is tracked separately and not communicated to the participants (Figure 4).

**Figure 4. Schedule of Work.** The amount of work required per reward increases geometrically. At most, 14 work-sets of a single type can be completed in the 2.5-hour voluntary self-administration interval. Thus, cumulative work will range up to 850 correct and 850 incorrect SDA trials performed. BrAC sampling or collection of subjective perceptions is performed during the 2.5 min required for reward delivery.

During a work set (below), the left-most symbol in the sequence is presented on the subject's monitor until the subject initiates a trial by pressing and holding down a 2-in diameter button (labeled here with the reward type "A" for alcohol, or "W" for the alternative reinforcer, water).

The press-and-hold causes an immediate display change: the outer ring of the symbol immediately turns from white to yellow signifying the onset of an anticipatory interval of unpredictable duration. Simultaneous with the change in outer ring color, an image will occupy the display, hiding the other visual stimuli (substituted for the reward indication for demonstration purposes). The subject may also be presented with a sound during this uncertainty interval. The nature of this image and sound will vary by session and reward – neutral for water and either neutral or aversive for alcohol dependent upon the session and selected from the International Affective Picture Scale, similar to our prior protocols (IRB # 1505788344). During this interval, the subject prepares to release the button as soon as the brief response window opens, indicated by color change of a random area of the image to blue. To count as a success, the subject must release the button within the response window; i.e. before the blue area disappears. Button release will terminate the display of the image. The SDA work task is adaptive: with success (green), the trial is counted towards the work-set requirement and the response window for the next trial is shortened; with failure (red), the response window lengthens; thus the overall success rate is specified independent of the effects of alcohol or fatigue.

Throughout any work-set, participants are free to wait, work *ad-lib*, pause, or cease working. The available rewards are a standardized increment in BrAC (alcohol, labeled "A") or an infusion of 30mL of half-normal saline (water, labeled "W"), each delivered over 2.5 min. Ethanol infusate is prepared by the Indiana University Research Pharmacy by mixing half-normal saline with 95% ethanol to create a 6.0% (v/V) solution. The Pharmacy monitors sterility and randomly checks infusate concentrations via gas chromatography. Delivery begins immediately after the last correct SDA trial required for the work-set is performed. Alcohol rewards raise the

participant's BrAC by 10.0 mg/dL in 2.5 min before declining at a steady rate of -0.8 mg/dL/min until the next alcohol reward is delivered. About every 10-15 min, and only during an alcohol reward delivery, participants complete a brief computer-assisted assay of craving for alcohol and subjective responses. Except for *ad-libitum* bathroom breaks, participants remain in the chamber or room for the duration of the experiment; technician interaction is limited to occasional BrAC samples and dependent-measure data collection. Upon completion of the alcohol self-administration interval, participants are served a 500-calorie lunch from the ICRC kitchen and remain in an inpatient room until no concerns regarding their ability to be safely discharged exist and at least 7:00 pm or until BrAC < 35 mg/dL and with no signs of intoxication, whichever is later. Subjects with a BrAC of 35 mg/dL or below but who show signs of intoxication and/or self-report any concerns regarding their safe passage home at the time of discharge will be provided transport home via car service. Participants that have to stay past 7:00 pm for the first and/or second session will be compensated at the rate of \$15/hour in 20 minute increments for the time stayed past 7:00 pm in a payment made at the second session. Any participants that stay past 7:00 pm for the first session will be informed that they have to stay until the same time for the second session (in order to reduce discharge motivated drinking behavior during the second session compared to the first). However, for the second session, participants will only actually be required to stay past 7:00 pm if their BrAC remains at or above 35 mg/dL with no signs of intoxication or a concern regarding their ability to be safely discharged exists. Participants will be offered a 1000 cal. dinner from the Indiana Clinical Research Center kitchen, *gratis*. Participants will be paid in cash upon discharge from each session, with an escalating payment schedule used to encourage retention.

Under rare circumstances, participants may express a need to leave the ICRC before protocol specified BrAC discharge criteria are met. For example, a participant may learn that a family member is seriously ill or requires care and indicates a need to leave to be with or assist the family member before the protocol stated BrAC level has been achieved. In these cases, the risk to the participant in the case of discharge must be balanced against the risks of remaining as well as their decision-making autonomy. The study staff will assess the situation and attempt to convince the subject to adhere to the protocol stated discharge criteria and discuss the situation with the PI or, if the PI is unavailable, a delegate investigator. If discharge is necessary or it is deemed the subject will simply attempt to leave without a formal discharge, study staff will implement the following procedure:

If the participant's BrAC is higher than the protocol-stated discharge criteria but less than 0.08 g% (80 mg/dL; the per se legal limit for driving under the influence) and without overt symptoms of intoxication, approval from the PI or delegate will be obtained. Participants will be strongly encouraged to allow study staff to arrange for the participant's transport via the participant's choice of a PI-approved method of transportation (for example, ride-share, taxi, pick-up by another adult, etc.) in lieu of driving themselves.

If the participant's BrAC is greater than or equal to 0.08 g% (80 mg/dL; the per se legal limit for driving under the influence) or the participant is subjectively determined to be intoxicated, the study team will implement Indiana CTSI Clinical Research Center Guidelines related to Study Participant and Visitor Behavior. Briefly, if the participant refuses a transportation option and indicates an intent to drive, they will be informed that IU Health Security may be called.

The team will attempt to follow-up with the participant following the event.

*EEG.* A 65-lead EasyCap® will be placed on the participant's head, with the resistance of every electrode maintained below 10K ohm. Scalp leads will be referenced to a lead taped on the bridge of the nose. The participant's EasyCap® will be connected to the input stage of Neuroscan Synamps2® EEG amplifier with output connected to a 24-bit analog-to-digital converter, sampled at 250 Hz. Three artifact leads will be calibrated for detection of eye-blink, eye-roll, frowning, swallowing, head-motion and heart-beat artifacts. Later, feedback-related ERPs will be produced using clean epochs of the continuous electrophysiological data record, defined by SDA feedback events inserted into the record.

*fMRI Acquisition.* Participants will be imaged in a recently installed Siemens 3T Magnetom Prisma MRI scanner equipped with a 64-channel head coil array using a multiband (MB) EPI sequence from the Center for Magnetic Resonance Research at the University of Minnesota. Prior to imaging, participants will be screened for fMRI safety, including drug, pregnancy, and BrAC screening. We will record the subject's recent drinking. They will be placed in the head coil with pads placed around their head and body for comfort. Scanning will take approximately 30 to 45 minutes and will include an MPRAGE sequence (provides high-resolution anatomical images for co-registration and normalization to the Montreal Neurological Institute (MNI) stereotactic coordinate system) and functional sequences, in which the participant will rest comfortably during the scan. Any discomfort by the participant will terminate imaging.

